8.2.3 Part 2 Sample Size

Part 2 is designed with a primary endpoint of OS. Approximately 350 patients will be randomized into Part 2 to obtain 247 death events (70% maturity). If the true OS HR for the comparison of varlitinib+capecitabine versus placebo+capecitabine is 0.7 (likely to correspond to a 43% prolongation of OS), the study has 80% power to demonstrate a statistically significant difference for OS, assuming a 2-sided 5% significance level.

Assuming non-linear recruitment of 350 patients over a twenty-four month period, and median OS times of 8.6 months and 6 months for the varlitinib and placebo arms respectively, it is estimated that 247 OS events will occur approximately 31 months after the first patient in for Part 2.

All secondary endpoints will be analyzed at the time of the primary analysis of OS.

8.3 Analysis Populations

8.3.1 Safety Population

For each part of the study, the safety population includes all patients in that part of the study who received at least 1 dose of randomized therapy (or study medication in the Safety lead-in) and will be the primary analysis set for the assessment of safety and tolerability in the study.

For the purpose of data summaries, patients will be included in the safety population according to the treatment arm and dose level initially received, regardless of any subsequent dose adjustments.

8.3.2 Full Analysis Set

For each part of the study, the full analysis set is based on the intention-to-treat principle and includes all randomized patients (or treated patients for the Safety lead-in) analyzed in accordance with the intended treatment arm, regardless of the treatment actually received.

With the exception of Part 1, Tumor Size which is not considered a key secondary endpoint (See Section 8.4.6 and 8.5.2.1), for all study parts, the primary analysis of all primary and key secondary efficacy endpoints, will be based on the full analysis set (FAS).

8.3.3 Evaluable for Response Set (Part 1 only)

The EFR set is defined as a subset of the FAS and includes patients with measurable disease at baseline, as determined by ICR assessments of radiological data based on the RECIST criteria, version 1.1. For Part 1 only, a sensitivity analysis of ORR and DCR will be performed in the evaluable for response (EFR) set to investigate the impact of patients without measurable disease on the primary endpoint. Since measurability is an inclusion criteria, all patients in Parts 1 should have measurable disease at baseline. Thus, if no patients were randomised in error, results in the EFR set will not be presented.

Since tumor size is an endpoint based on patients' tumor measurements, it can only be defined for the subset of the FAS with measurable disease at baseline. Thus the EFR set will be the primary analysis set used for the assessment of tumor size for Part 1 (See Section 8.4.6).

8.3.4 Per Protocol Analysis Population

The per protocol (PP) analysis population is defined for Part 1. Efficacy is not the focus of the Safety lead-in and Part 2 will be assessed on an intention-to-treat basis only. Thus PP analyses are not required for the Safety lead-in and Part 2 of the study.

The PP analysis population will include all randomized patients according to the treatment actually received, and excluding any patients with major deviations. Major deviations that would lead to exclusion from the PP analysis population include:

- Patients who did not have the intended disease (failure of inclusion criteria 2)
- Subjects who did not have the intended indication, i.e. were not second line patients (failure of inclusion criteria 3)
- Patients who did not received any randomized therapy
- Patients with baseline radiological scan performed before the start of protocol-specified interval prior to randomization
- Patients who did not have measurable disease at baseline as determined by ICR
- Subjects who have not received at least six doses of gemcitabine in a first line setting (i.e. failure of inclusion criteria 4, protocol version 4.0 onwards)

- Subjects with multiple (≥ 2) peritoneal metastases at baseline or ascites at baseline which cannot be attributed to a non-malignant cause (i.e. failure of exclusion criteria 3, protocol version 4.0 onwards), based on ICR review
- Subjects with baseline albumin < 3 g/dL (failure of the albumin component of inclusion criteria 9c)

In addition to the programmatic determination of the major deviations, monitoring notes or summaries will be reviewed to determine any important post entry deviations that are not identifiable via programming, and to check that those identified via programming are correctly classified. The final classification will be made blinded, prior to database lock.

Patients who received the incorrect randomized therapy should be included in the PP analysis set according to the therapy actually received. Similarly, subjects who were mis-stratified at randomization will be included in the PP analyses according to the correct stratification levels, regardless of the levels declared at randomization.

Failure of an inclusion/exclusion criterion will not automatically be classified as a major deviation.

The PP analysis population will be used to assess the sensitivity of the Part 1 ORR, DoR, DCR, PFS and OS analyses to major deviations.

8.3.5 PK Analysis Set

The PK population contains all patients who have been dosed with varlitinib and provided at least one usable PK profile. All PK data will be analyzed according to treatment received.

For the Safety lead-in, this population will comprise all data patients who receive study treatment as per protocol (300 mg BID) and did not violate or deviate from the protocol and planned dosing regimen (300 mg) in ways that would significantly affect the PK analyses (for example skipping doses, or taking reduced doses or taking concomitant medications with the potential to cause a drug-drug interaction) during the PK sampling period. Patients who did deviate from the planned dosing regimen may still provide some data for inclusion in the PK set if they have at least one usable PK profile. The population, and decisions regarding which profiles are usable, will be defined by the Study Team Physician, Pharmacokineticist, and Statistician prior to any analyses being performed.

PK sampling of all patients is planned for Part 1 the study, while sparse PK sampling is planned for Part 2. The number of patients who will provide samples in Part 2 for the PK analysis will be defined based on the results of Part 1 of the study. All PK data will be analyzed according to the treatment received. Deviations that have the potential to significantly affect the PK will be reviewed, and patients, or specific PK profiles for a patient, may be excluded from the PK set if appropriate. The population, and decisions regarding which profiles are usable, will be defined by the Study Team Physician, Pharmacokineticist, and Statistician. Since the PK sample analysis may be performed following the primary analyses of efficacy, the CRO responsible for the analysis of the

PK samples will mask the subject ID prior to any discussion regarding deviations, in order to ensure that decisions regarding which samples to include/exclude from the PK set are made blinded to clinical outcomes.

Population PK models may be used to derive the PK parameters.

Table 14: Summary of Outcome Variables and Analysis Populations

Outcome Variable	Analysis Population (Sensitivity Analysis Population)
Efficacy Data (Primary and key secondary endpoints)	
ORR, DCR	FAS (EFR and PP Part 1 only)
PFS, OS, DoR	FAS (PP Part 1 only)
Part 1 ORR based on site data	FAS
Part 1 Tumor size ¹	EFR
Demography	FAS
Pharmacokinetics	
PK	PK
Safety	
Exposure	Safety
Adverse Events	Safety
Laboratory measurements	Safety
Vital Signs	Safety
ECG	Safety
Physical Examination	Safety

¹ Tumor size, by definition, is only defined in patients with measurable disease. For marketing authorization, no statistical claims will be based on tumor size (See Section 8.5.2.1).

Abbreviations: DCR = disease control rate, DoR = duration of response, ECG = electrocardiogram, EFR = evaluable for response, FAS = full analysis set, ORR = objective response rate, OS = overall survival. PFS = progression- free survival, PK = pharmacokinetics, PP = per protocol

8.4 Study Endpoints

8.4.1 Objective Response Rate

Objective response rate is a co-primary endpoint in Part 1 and a secondary endpoint in Part 2, and the Safety lead-in cohort.

Objective response rate is defined as the number (%) of patients with at least one visit response of CR or PR. Data obtained up until progression, or last evaluable assessment

in the absence of progression, will be included in the assessment of ORR. This will be irrespective of whether or not patients discontinued treatment or received a subsequent therapy prior to progression. For all study parts, ORR will be evaluated based on the FAS set ([Section 8.3.2](#)).

8.4.2 Progression-Free Survival

Progression-free survival is a co-primary endpoint in Part 1, and is a secondary endpoint in Part 2.

Progression-free survival is defined as the time from randomization (or start of treatment in the Safety lead-in) until the date of objective disease progression or death (by any cause in the absence of disease progression) regardless of whether the patient withdraws from randomized therapy (study treatment in the Safety lead-in) or receives another antitumor therapy prior to disease progression. Patients who have not experienced disease progression or died at the time of analysis will be censored at the time of the latest date of assessment from their last evaluable RECIST assessment. However, if the patient progresses or dies after 2 or more missed visits, the patient will be censored at the time of the latest evaluable RECIST version 1.1 assessment.

The PFS time will always be derived based on the scan/assessment dates rather than visit dates and the following rules will be applied:

- Date of disease progression will be determined based on the earliest of the dates of the component that triggered the disease progression, i.e., if both the target lesions and the non-target lesions indicate disease progression but were scanned on different days, the earlier of the 2 dates would be applied.
- When censoring a patient for PFS, the patient will be censored at the latest of the dates contributing to a particular overall visit assessment.

For Part 1, the co-primary endpoint, PFS, will be derived programmatically using data from the ICR. To support sensitivity analyses, PFS will also be derived programmatically using the site assessments of the Part 1 radiological data.

For Part 2 and the Safety lead-in, PFS will be derived programmatically using the site radiological data.

Further details will be provided in the SAP.

8.4.3 Overall Survival

Overall survival is a secondary endpoint in Part 1, and the primary endpoint in Part 2 of the study.

Overall survival is defined as the time from the date of randomization until death due to any cause. Any patient not known to have died at the time of DCO will be censored based on the last recorded date on which the patient was known to be alive.

Note, survival calls may be made in the week following the date of DCO for the analysis, and if patients are confirmed to be alive or if the death date is after the DCO these patients will be censored at the date of DCO.

8.4.4 Duration of Response

Duration of response is secondary endpoint in all study parts.

The DoR is defined as the time from the date of first documented response until the date of documented disease progression or death in the absence of disease progression. The end of response should coincide with the date of disease progression or death from any cause used for the PFS endpoint. For Part 1, DoR will be calculated using the ICR data, and for Part 2 and the Safety lead-in, DoR will be calculated from the site radiological data.

The time of the initial response will be defined as the latest of the dates contributing towards the first visit response of PR or CR. For example, if the patient was first noted to have a PR at week 6, and the target and non-target lesions were assessed on different dates at this visit, then the later of the 2 assessment dates would be used as the start date of the response.

If a patient does not progress following a response, then their DoR will use the PFS censoring time.

Duration of response will not be defined for those patients who do not have documented response.

8.4.5 Disease Control Rate

Disease control rate is a secondary endpoint in all study parts.

Disease control rate is defined as the number (%) of patients with at least one visit response of CR or PR, or with stable disease for a minimum of twelve weeks (± 5 days) from randomization (Parts 1 and 2) or starting treatment (Safety lead-in only). Data obtained up until progression, or last evaluable assessment in the absence of progression, will be included in the assessment of DCR. This will be irrespective of whether or not patients discontinued treatment or received a subsequent therapy prior to progression. For all study parts, DCR will be evaluated based on the FAS set ([Section 8.3.2](#)). For Part 1, DCR will be calculated based on the ICR data. For Part 2 and the Safety lead-in, DCR will be calculated from the site radiological data.

8.4.6 Tumor Size

The percentage change from baseline in tumor size at Week 12 ($\% \Delta TS_{Wk12}$) is a secondary endpoint for Part 1, and will be used to help evaluate the exploratory objectives of investigating the possible role of baseline biomarker levels as predictors of clinical benefit. It will be evaluated using the Evaluable for Response set (EFR) ([Section 8.3.3](#)). Tumor size is not considered to be a key secondary endpoint; for the purpose of marketing authorization, no statistical claims will be made based on tumor size.

The $\% \Delta TS_{Wk12}$ will be defined as follows:

- Baseline tumor size: defined as the sum of longest diameters of target lesions at baseline
- Week 12 TS: defined as the sum of longest diameters of target lesions at week 12

$$\% \Delta TS_{Wk12} = 100 \times \frac{Week\ 12\ TS - Baseline\ TS}{Baseline\ TS}$$

An increase from baseline of 20% will be imputed for any patients who die by any cause, or withdraw from the study due to symptomatic disease progression prior to Week 12. Any patients who withdraw from the study due to radiological disease progression prior to Week 12 will be included in the analysis, and will be assigned a percentage change from baseline of 20%, or the value that was observed at the time of disease progression (whichever is larger). Full details of data imputation rules will be provided in the SAP.

8.4.7 Safety Endpoints

Patient safety will be evaluated based on physical examination, vital signs (blood pressure [systolic and diastolic], heart rate, respiratory rate, and body temperature), ECG parameters, clinical laboratory tests (hematology, clinical chemistry, coagulation, and urinalysis), and AEs.

8.4.8 ECG Parameters

The ECG parameters of interest are QT including QTcF and QTcB, HR (heart or ventricular rate), PR, and QRS intervals.

8.5 Methods of Statistical Analysis

8.5.1 Primary Endpoints

8.5.1.1 Part 1 - Objective Response Rate

The primary analysis will test for the superiority of varlitinib-containing treatment arm relative to the placebo-containing arm.

Objective response rate will be analyzed using a stratified exact binomial test^{16,17} that extends Fisher's Exact test to more than one stratum. The analysis will be stratified by

primary tumor location (gallbladder/NonGB). The 2-sided p-value will be obtained by doubling the 1-sided p-value.

The conditional maximum likelihood estimate of the odds ratio will be presented together with its exact 2-sided 95% confidence limit, which excludes one if and only if the stratified exact binomial test is significant at a 2-sided 5% level. Corresponding significance levels and confidence intervals (CIs) will be calculated using tests performed at a 1-sided 10% level. The 1-sided p-value will also be presented.

To test for heterogeneity across strata, the exact test of Zelen¹⁸ will be performed testing whether the treatment effect differs between the 2 strata included in the primary analysis.

For Part 1 only, subgroup analyses will be conducted comparing ORR between treatments in the subgroups of the FAS set defined by the stratification factors declared at randomization, Region (US/Non-US) and primary tumor location (GB/Non-GB), plus the following factors:

- Gender (male vs female)
- Race (Asian/Caucasian/Other)
- Baseline ECOG status (0/1)
- Extent of disease (locally advanced/metastatic)
- Age (<60/>=60)
- Baseline HER2 expression (positive defined as +++ or above by IHC, otherwise negative)
- Any HER positivity (positive defined as + or higher by IHC for HER1, HER2, HER3, HER4, or otherwise negative)

Note: The sub-group analyses based on IHC biomarker data will be reported outside of the main CSR.

Other baseline variables may also be included if there is clinical justification or an imbalance is observed across the treatment arms. For each sub-group, the odds ratio and corresponding 80% CI will be presented on a forest plot including the odds ratio and 80% CI from the overall population. Additionally, if the primary analysis of ORR is significant at the 2-sided 5% level in the overall population, the forest plot will be replicated using 95% CI.

No adjustment to the significance level for testing will be made since all these analyses will be considered supportive of the primary analysis of ORR.

8.5.1.2 Part 1 – Progression-Free Survival

In Part 1, the primary analysis will test for the superiority of varlitinib-containing treatment arm relative to the placebo-containing arm, as assessed by PFS. The DCO for the primary analysis of PFS will be the later of 12 weeks after last patient in and 84th documented PFS event.

Progression-free survival will be analyzed using a stratified log-rank test using the Breslow method to handle ties.¹⁹ The stratification factor is primary tumor location (GB/Non-GB). The results will be presented in terms of the HR (with a HR <1 favoring the varlitinib-containing arm) and associated 2-sided 95 CI and 2-sided p-value. For Part 1 only, the 80% CI and 1-sided p-value will also be presented. The HR and its CI can be estimated from the log-rank as follows^{20,21,22}:

$$\text{HR} = \exp(U/V)$$

$$95\% \text{ CI for HR} = (\exp\{U/V - 1.96/\sqrt{V}\}, \exp\{U/V + 1.96/\sqrt{V}\})$$

Where $U = \sum_k U_k = \sum_k \sum_i (d_{1ki} - e_{1ki})$ is the stratified log-rank test statistic obtained from the SAS LIFETEST procedure, $\sqrt{V} = \sqrt{\sum_k V_k}$, is its standard deviation, k denotes the stratum and d_{1ki} and e_{1ki} are the observed and expected events in group 1, stratum k .

Kaplan-Meier (KM) plots of PFS, with tick marks to identify censored observations, will be presented by treatment group. Summaries of the number and percentage of patients experiencing a PFS event, and the type of event (RECIST 1.1 or death) will be provided along with median PFS for each treatment.

The assumption of proportionality will be assessed.

For Part 1 only, subgroup analyses will be conducted comparing PFS between treatments in the subgroups of the full analysis set defined by the stratification factors declared at randomization, Region (US/Non-US) and primary tumor location (GB/Non-GB), plus the following factors:

- Gender (male vs female)
- Race (Asian/Caucasian/Other)
- Baseline ECOG status (0/1)
- Extent of disease (locally advanced/metastatic)
- Age (<60/>=60)
- Baseline HER2 expression (positive defined as +++ or above by IHC, otherwise negative)
- Any HER positivity (positive defined as + or higher by IHC for HER1, HER2, HER3, HER4, or otherwise negative)

Note: The sub-group analyses based on IHC biomarker data will be reported outside of the main CSR.

Other baseline variables may also be assessed if there is clinical justification. For each subgroup, the HRs (varlitinib: placebo) and associated CIs will be calculated from a log rank test within each individual subgroup. These will be presented on a forest plot including the HR and 80% CI from the overall population. The purpose of the subgroup

analyses is to assess the consistency of treatment effect across expected and possible prognostic factors.

No adjustment to the significance level for testing will be made since all these analyses will be considered supportive of the primary analysis of PFS.

For both Part 1 and Part 2, Cox proportional hazards modeling will be employed to assess the effect of covariates on the HR estimate. Before embarking on more detailed modeling, an initial model will be constructed, containing treatment and the stratification factor primary tumor location alone, to ensure any output from the Cox modeling is likely to be consistent with the results of the stratified log-rank test.

The presence of quantitative interactions will be assessed formally by means of an overall global interaction test. This will be performed in the full analysis set by comparing the fit of a Cox proportional hazards model including treatment, all covariates, and all covariate-by-treatment interaction terms, with one that excludes the interaction terms and will be assessed at the 2-sided 10% significance level. If the fit of the model is not significantly improved then it will be concluded that overall the treatment effect is consistent across the subgroups.

If the global interaction test is found to be statistically significant, an attempt to determine the cause and type of interaction will be made. Stepwise backwards selection will be performed on the saturated model, whereby (using a 10% 2-sided level throughout) the least significant interaction terms are removed one-by-one and any newly significant interactions re-included until a final model is reached where all included interactions are significant and all excluded interactions are non-significant. Throughout this process all main effects will be included in the model regardless of whether the corresponding interaction term is still present. This approach will identify the factors that independently alter the treatment effect and prevent identification of multiple correlated interactions.

Any quantitative interactions identified using this procedure will then be tested to rule out any qualitative interaction using the approach of Gail and Simon.²³

The primary analysis of PFS will be based on the programmatically derived PFS based on an ICR of radiological data and using all scans regardless of whether they were scheduled or not. To assess the potential impact of informative censoring on the primary analysis of PFS, a sensitivity analysis using PFS derived from site assessments will be performed. Full details of the planned sensitivity analyses will be provided in the SAP.

The primary analysis will be performed on the FAS.

Patients whose data contributed to the Part 1 analysis will not contribute to the Part 2 analysis.

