5.3 Selection of Study Population

5.3.1 Number of Planned Patients

Safety lead-in:

A total of 12 to 20 eligible patients will be enrolled to receive varlitinib plus capecitabine.

United States: 6 to 12 eligible patients are expected to be enrolled from the United States.

Rest of the World: An additional 6 to 8 eligible patients will be enrolled from the rest of the world.

Patients in this group will be replaced if investigational product compliance is < 85% in the first 14 days. Pharmacokinetic sampling will be performed in approximately 12 patients.

Part 1:

Approximately 120 eligible patients will be enrolled and randomized in a 1:1 ratio to receive varlitinib and capecitabine (n=60) or placebo and capecitabine (n=60).

Part 2:

Approximately 350 eligible patients will be enrolled and randomized in a 1:1 ratio to receive varlitinib and capecitabine (n=175) or placebo and capecitabine (n=175).

In both Part 1 and Part 2 of the study, patients will be stratified by:

- region - US and the rest of world (ROW) and;
- primary tumor location - gallbladder vs non-gallbladder.

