7.1.2.2 Cancer Antigen Evaluation

For Part 1 and 2 of the study, blood will be collected for analysis of CA19.9 and carcinoembryonic antigen (CEA) at screening and every 6 weeks (± 5 days) from Cycle 1 Day 1. Collection of blood for these analysis stops at EOT.

Archival paraffin-embedded tumor tissues will be collected during screening for future analysis if the patient has provided the optional tumor tissue consent.

Biopsies will be performed during screening for those patients who did not have enough archival tumor tissue if the patient has provided the optional tumor tissue consent.

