- Baseline ECOG Status
- Extent of Disease (Locally Advanced/Metastatic)
- Age (<60/>=60)
- Baseline HER2 expression (positive defined as +++ or above by IHC, otherwise negative)
- Any HER positivity (positive defined as + or higher by IHC for HER1, HER2, HER3 or HER4, otherwise negative)

Other baseline variables may also be assessed if there is clinical justification. For each subgroup, the HRs (varlitinib: placebo) and associated CIs will be calculated from a log rank test within each individual subgroup. These will be presented on a forest plot including the HR and 80% CI from the overall population. Additionally, if the primary analysis of PFS is significant at the two-sided 5% level in the FAS, the forest plot will be replicated using 95% confidence intervals.

The purpose of the subgroup analyses is to assess the consistency of treatment effect across expected and possible prognostic and predictive factors. No adjustment to the significance level for testing will be made since all these analyses will be considered supportive of the primary analysis of PFS.

For both Part 1 and Part 2, Cox proportional hazards modeling will be employed to assess the effect of covariates on the HR estimate. Before embarking on more detailed modeling, an initial model will be constructed, containing treatment and the two stratification factors alone, to ensure any output from the Cox modeling is likely to be consistent with the results of the stratified log-rank test.

The presence of quantitative interactions will be assessed formally by means of an overall global interaction test. This will be performed in the full analysis set by comparing the fit of a Cox proportional hazards model including treatment, all covariates, and all covariate-by-treatment interaction terms, with one that excludes the interaction terms and will be assessed at the 2-sided 10% significance level. If the fit of the model is not significantly improved then it will be concluded that overall the treatment effect is consistent across the subgroups.

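### The 10% global interaction test rejects too often in Part 1, and its non-significant result cannot be reported as a consistent treatment effect

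*Protocol*

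**What the plan says.** Protocol 8.5.1.2 and SAP 7.2 describe one global test in the full analysis set, "comparing the fit of a Cox proportional hazards model including treatment, all covariates, and all covariate-by-treatment interaction terms", against the same model without the interactions. The test "will be assessed at the 2-sided 10% significance level". A non-significant result has a fixed consequence: "it will be concluded that overall the treatment effect is consistent across the subgroups". A significant result starts backward selection at 10%, and then "Any quantitative interactions identified using this procedure will then be tested to rule out any qualitative interaction", using the Gail-Simon method.

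The procedure covers Parts 1 and 2. Protocol 8.5.1.3 and SAP 7.3 carry the PFS methods over to OS in Part 2.

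Neither document says which covariates enter this model. The nearest list is the subgroup list in the same sections: region, tumour location, gender, race in three levels, ECOG, extent of disease, age, HER2 expression and any-HER positivity. The Protocol adds that "The sub-group analyses based on IHC biomarker data will be reported outside of the main CSR"; SAP 7.2 has the same factors without that note. Tumour tissue, on which HER status depends, is collected only "if the patient has provided the optional tumor tissue consent" (Protocol 7.1.2.2).

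**The concern.** With this many terms and this few events, the chi-square reference for a likelihood-ratio comparison of Cox models is unreliable. If the true level is well above 10%, the plan will often start a stepwise search for an interaction that does not exist.

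The other branch fails for a different reason. Failure to reject is not evidence of similarity, yet both documents turn it into a positive finding. A reader of the Part 1 PFS result, or of OS in Part 2, could be told that the effect is consistent on the strength of a test with little ability to show otherwise. The wording about ruling out a qualitative interaction has the same fault.

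**Working it through.** **1. The plan's own figures.** Power = Φ(√d/2 × |ln HR| − z).

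- 84 events, HR 0.54, two-sided 5%: 4.583 × 0.6162 − 1.960 = 0.864, so 80.6%.
- 84 events, HR 0.58, one-sided 5%: 4.583 × 0.5447 − 1.645 = 0.851, so 80.3%.
- 247 deaths, HR 0.70, two-sided 5%: 7.858 × 0.3567 − 1.960 = 0.843, so 80.0%.

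The stated figures reproduce. For the interaction test the documents give only the nominal level.

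**2. Size of the model.** Eight binary factors plus three-level race give 8 + 2 = 10 interaction df. The full model has 1 + 10 + 10 = 21 coefficients, so 84/21 = 4.0 events per coefficient. Without the two HER factors there are 8 df and 1 + 8 + 8 = 17 coefficients, so 84/17 = 4.9. Part 2 with 10 df has 247/21 = 11.8.

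**3. Inputs to the simulation.** From the documents: "Approximately 120 eligible patients will be enrolled and randomized in a 1:1 ratio" (Protocol 5.3.1); 84 events, control median PFS 2.67 months, HR 0.54 and 8-month non-linear recruitment (Protocol 8.2.2); about 20% US patients (Protocol 5.2); gallbladder share near one half (SAP 6.7). Assumed: exponential PFS, quadratic accrual, and the other prevalences. These were either all balanced or an uneven mix (Other race 5%, metastatic 85%, HER2-positive 10%, any-HER positive 90%). The likelihood-ratio statistic was compared with the chi-square 10% point (15.99 on 10 df). Part 1 scenarios in the table had 1500-2000 runs (standard error about 1 point); Part 2 had 800.

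**4. Rejection rate when there is no interaction (nominal 10%).**

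| Scenario | Rejects |
|---|---|
| Part 1, 10 df, balanced factors | 22-23% |
| Part 1, 10 df, uneven mix | 25-26% |
| Part 1, 10 df, sparser factors | 27% |
| Part 1, 10 df, six-week scans varied by ±5 days | 21-23% |
| Part 1, 10 df, uneven mix, 100 events | 27% |
| Part 1, 8 df | 16-19% |
| Part 2, 10 df | 13-15% |

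Further runs under other assumptions widen the Part 1 ranges to 20-27% (10 df) and 16-20% (8 df). With 10 df the simulated 90th percentile is about 20.0; that value, not 15.99, would give a true 10% level.

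**5. What a non-significant result misses (Part 1, 10 df, test as written).** HR 0.40 against 1.00 is a ratio of 1.00/0.40 = 2.5. In a balanced factor it is detected in 46-51% of runs, so it is missed about half the time. Other balanced cases:

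| Ratio of hazard ratios | Missed |
|---|---|
| 2-fold | 60% |
| 3-fold | 40-44% |
| 4-fold | 26-29% |
| 6-fold | 9% |

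A 4-fold ratio confined to a 10% subgroup is missed 53% of the time.

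**6. Precision for a single factor.** If 84 events split evenly over the four treatment-by-level cells, the variance of the log ratio of hazard ratios is about 4/21 = 0.190, with standard error 0.436. The 95% interval spans a factor of exp(1.96 × 0.436) = 2.35 each way. An estimate of exactly 1 would still be compatible with ratios from about 0.43 to 2.35.

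**The case against.** **The level depends on tied times.** If every PFS time fell exactly on the six-week grid and the Cox model used Breslow ties, the test would be conservative, at about 6%. The documents do not describe such data. Scans have a ±5-day window, PFS uses actual scan dates, deaths count as events and unscheduled scans are included. With dates varied by ±5 days the rate returns to 21-23%. Tie handling is stated for the log-rank test but not for this model.

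**The covariate list is not fixed.** This stands. A reader might take one figure, such as 23%, as a property of the plan. It is not: the 8-df reading is at least as plausible for the main report, given the Protocol's note on IHC subgroups. A reader might also cite about 32%, which arises if the HER terms stay in and only 80 or 90 of 120 patients have complete data. No document gives a tissue rate, so that is a warning, not a finding.

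**Extreme interactions.** A reader might infer that the test misses these half the time. The 2.5-fold ratio is missed that often; balanced 4-fold and 6-fold ratios are missed 26-29% and 9% of the time.

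**A smaller test.** Restricting the test to the two stratification factors (2 df) brings the level to about 10-11%, and it detects HR 0.40 against 1.00 by tumour location 58% of the time. A reader might infer that it is at least as sensitive in general. It is not. For the same interaction by gender it detects 10-12%, essentially its false-positive rate, against 48-51% for the 10-df test.

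**Limited consequences.** This stands too. The subgroup analyses are declared supportive, forest plots show every subgroup hazard ratio with its interval, and a false positive leads to labelled follow-up rather than an efficacy claim.

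**Conclusion.** The point holds in a limited form. If the covariates are the listed subgroup factors and the chi-square reference is used, the nominal 10% test rejects under no interaction about 20-27% of the time in Part 1 with 10 df, 16-20% with 8 df, and 13-15% in Part 2. These ranges assume prevalences that the documents do not give, and scan times not all exactly on the grid.

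The mandated conclusion of consistency is unsound whatever the simulated figures, and the 2.5-fold example shows the practical size of the problem. The excess in Part 2 is modest. Nothing here touches the co-primary tests or their type I error, and nothing in the documents supports reading it as a threat to the main efficacy conclusion.

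**What to change.** In Protocol 8.5.1.2 and SAP 7.2:

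- Name the covariates in the global test: the seven prespecified non-IHC factors (8 df). Keep the HER factors in the separate biomarker report.
- Take the p-value from a resampling reference, for example a parametric bootstrap under the main-effects model or a suitable permutation scheme, with the same tie handling as the fitted model, so that the 10% level is met.
- Replace the conclusion of consistency with a statement that no evidence of heterogeneity was detected.
- Say that the Gail-Simon step tests for qualitative interaction, not that it rules it out.
- Report the ratio of hazard ratios with a confidence interval for each factor.

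Do not cut the test down to the two stratification factors, since that leaves almost no power for the others.

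The cost is wording, minor programming and some power. With the 10-df test held to a true 10%, detection of a balanced 4-fold ratio falls from 71-74% to about 54%, and a 2-fold ratio is detected about 22% of the time. That loss is the price of the stated level, and it is a further reason to rely on the intervals.
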